1 PROTOCOL SUMMARY

Trial Title	A randomized, double-blind, placebo-	controlled, 2-way cross-over trial evaluating the		
	pharmacodynamic effect of C21 on end	dothelial dysfunction and safety in subjects with type		
	2 diabetes mellitus			
Trial ID	VP-C21-013			
Trial Phase	1b			
Objectives and	Objectives	Endpoints		
Endpoints	Primary			
	To evaluate the pharmacodynamic effe	ect of • Reactive hyperemia index (RHI) score as		
	a single oral dose of 200 mg C21 versu			
	placebo on endothelial dysfunction in	***		
	subjects with type 2 diabetes mellitus			
	(T2DM)			
	Secondary			
_				
Trial Design	This is a randomized, double-blind, pla	acebo-controlled, 2-way cross-over trial to evaluate		
	· ·	endothelial dysfuction and safety in subjects with		
	T2DM.			
	The subjects will have 4 visits at the tr	ial site:		
	 Visit 1: Screening will take place within 3 weeks of the planned first IMP 			
		and will include the subject's signing of the		
	informed consent and an eligibili	# C		
		t the trial site for single-dose, oral IMP administration		
		domization list), safety and pharmacodynamic		
	between visits 2 and 3.	There will be a washout period of 3 to 14 days		
	Activities of the parties of the par	-114-1		
	withdrawal from trial.	will take place 5 to 14 days after Visit 3 or after early		
Number of		sed subjects, with 12 being the target number.		
	The dial will include 10 to 14 fandomi	sed subjects, with 12 being the target humber.		
Subjects Inclusion Criteria	For inclusion in the trial, subjects must	fulfil the following criterie:		
inclusion Criteria	4000 100000 W N N N N	Miles concentrate organic market forms of the second		
	Written informed consent, consist before the initiation of any trial-re-	tent with ICH-GCP R2 and local laws, obtained elated procedure.		
	 Male or female patient aged ≥ 40 	years at the time of the screening visit (Visit 1).		
	The state of the s	OM prior to the screening visit (Visit 1).		
	A management of the company of	EndoPAT at the time of the screening visit (Visit 1).		
>	i) Illian score 32 as assessed by I	moorale at the time of the serecting visit (visit 1).		

Clinical Trial Protocol

Vicore Pharma ABVersion: 2.0Trial ID: VP-C21-013Date: 03-MAR-2023

	5) Contraceptive use by men and women of childbearing potential which is highly effective and consistent with local regulations regarding the methods of contraception for those participating in clinical trials.	
Exclusion Criteria	Subjects must not enter the trial if any of the following exclusion criteria are fulfilled:	
	 Concurrent serious medical condition which in the opinion of the investigator constitutes a risk or a contraindication for the participation in the trial or that could interfere with the trial objectives, conduct or evaluation. 	
	2) Known, active hepatitis B, C, or human immunodeficiency virus (HIV) infection (i.e. , HIV with a CD4 count <500 cells/mm ³).	
	 Impaired hepatic function or clinically significant liver disease, which in the investigator's opinion makes the subject inappropriate for this trial. 	
	 Severe renal impairment (i.e., estimated glomerular filtration rate (eGFR) ≤30 mL/min/1.73 m²). 	
	5) Prolonged QTcF (QT interval with Fridericia's correction) (>450 ms), atrial fibrillation, clinically significant arrhythmia or other clinically significant abnormality in the resting ECG at screeening (Visit 1), as judged by the investigator.	
	Unstable or deteriorating cardiac condition.	
	7) History of severe allergy/hypersensitivity or ongoing allergy/hypersensitivity, as judged by the investigator, or history of hypersensitivity to drugs with a similar chemical structure or class to any of the IMPs.	
	8) Pregnant or breast-feeding female subjects.	
	 Malignancy within the past 5 years with the exception of in situ removal of basal cell carcinoma and cervical intraepithelial neoplasia grade I. 	
	10) Planned major surgery within the duration of the trial.	
	11) Treatment with the medications listed below within 14 days prior to screening (Visit 1) or anticipated need for such medication during the participation in this trial:	
	Insulin.	
	 Glucagon-like peptide-1 (GLP-1) agonists. 	
	 Strong Cytochrome P450 (CYP) 3A4 inducers (e.g., rifampicin, phenytoin, carbamazepine and St. John's Wort). 	
	 Strong CYP 3A4 inhibitors (e.g. clarithromycin, ketoconazole, nefazodone, itraconazole, ritonavir). 	
	 Warfarin, digoxin and other medication where the dose needs to be individually titrated. 	
	 Narrow therapeutic index drugs that are substrates of CYP1A2, CYP2C8, CYP2C9, CYP2C19, CYP3A4, or OATP1B1. 	
	12) Current or previous participation in any other clinical trial where the subject has received a dose of IMP within 1 month or 5 half-lives of the IMP, whichever is longest, prior to screening.	
]	13) Abnormal laboratory value at screening indicating a potential risk for the subject if enrolled in the trial as evaluated by the investigator.	
Investigational	C21	
dosage and mode	C21 is supplied as a 50 mg capsule for oral administration. C21 200 mg (4 capsules) will be administered as a single oral dose.	
of administration	Placebo to C21	

Vicore Pharma AB
Version: 2.0
Trial ID: VP-C21-013
Date: 03-MAR-2023

	Placebo to C21 is supplied as a capsule for oral administration, manufactured as C21 without the active pharmaceutical ingredient. Placebo to C21 (4 capsules) will be administered as a single oral dose.
Criteria for Evaluation	All subjects who have received at least one dose of IMP will be included in the safety analyses. The pharmacodynamic analyses (assessed by EndoPAT) will include all treated subjects for whom the pharmacodynamic parameters can be calculated.
Statistical Analyses	All quantitative variables will be summarized by assigned treatment and time point using standard descriptive statistics. Qualitative variables will be summarized by assigned treatment and time point by means of absolute and relative frequencies.
	Percentage change in RHI will be compared between treatments using an analysis of variance model adjusting for treatment, period, and subject (random).
Sample Size Calculation	Sample size is based on what is usually seen in this type of trial and not on any statistical assumptions.
Trial Reporting	After completion of the trial, an International Council for Harmonisation (ICH) E3 guideline-compliant clinical trial report (CTR) will be prepared.

Vicore Pharma AB Version: 2.0 Trial ID: VP-C21-013 Date: 03-MAR-2023

2 FLOW CHART

Table 1 Flow Chart for Trial Procedures

	CTP section	Screening	Trial Intervention Visits		Follow-up/end-of- trial ¹
		Visit 1	Visit 2	Visit 3	Visit 4
		Day -21 to Day -1	Day 1	3 to 14 days after Visit 2	5-14 days after Visit 3
Informed consent	8.1.1	X			
Eligibility criteria	8.1.2	x	x^2	x^2	
Demographics	8.1.3	x			
Height and weight	8.1.4	x			
Medical/surgical history	8.1.5	X			
12-lead ECG	8.1.6	x	x^3	x^3	x
Pharmacodynamic (EndoPAT) assessment ⁴	8.2.1	x	x	x	
Adverse events ⁵	8.3.1			X	
Pregnancy test (urine dipstick) ⁶	8.3.2	x	X	х	X
Physical examination ⁷	8.3.3	x	x	х	x
Vital signs	8.3.4	x	x	х	x
Laboratory safety assessment	8.3.5	x			x
FSH ⁸	8.3.5	x			
Prior and concomitant medication	8.4.1			X	
Randomisation	7.3		x		
IMP administration9	7.4		X	X	

BMI=body mass index, CTP=clinical trial protocol, ECG=electrocardiogram, FSH=follicle stimulating hormone, IMP=investigational medicinal product.

- 1. Or after early withdrawal.
- Confirmation of relevant eligibility criteria.
 At Visits 2 and 3, a 12-lead ECG will be collected within 60 minutes prior to IMP administration and before initiation of the EndoPAT assessment, 50±10 minutes after the IMP administration.
- At Visits 2 and 3, the EndoPAT assessment will be performed 50±10 minutes after the IMP administration.
- 5. Adverse events will be recorded from signing informed consent until end of trial (Visit 4).
- 6. Applicable only in women of childbearing potential. If positive, the urine dipstick will be followed-up by a blood test.
- 7. A physical examination will be done at Visits 1 and 4. Symptom-driven physical examination will be done upon admission and discharge from the trial site at Visits 2 and 3.
- 8. Applicable only in postmenopausal females.
- 9. C21 or placebo will be administered at Visits 2 and 3, respectively, according to the randomisation list.

Clinical Trial Protocol

Vicore Pharma AB Version: 2.0 Trial ID: VP-C21-013 Date: 03-MAR-2023

3 BACKGROUND AND RATIONALE

3.1 Endothelial Dysfunction

The endothelium is a monolayer of cells that lines all blood vessels, and which comprises the systemic and lymphatic capillaries. The vascular endothelium is an active paracrine, endocrine, and autocrine organ that regulates the vascular tone and maintains vascular homeostasis.

The basic mechanisms involved in atherogenesis indicate that deleterious alterations of endothelial physiology, otherwise known as endothelial dysfunction, represent a key early step in the development of atherosclerosis and are also involved in plaque progression and the occurrence of atherosclerotic complications.

Endothelial dysfunction is the single most important factor for increased cardiovascular risk in patients with type 2 diabetes mellitus (T2DM).

3.2 Current Treatment of Endothelial Dysfunction

Non-pharmacological therapies involve diet control and exercise. Pharmacological treatment of patients with T2DM and endothelial dysfunction includes metformin, peroxisome proliferator-activated receptor— γ (PPAR- γ) agonists and concomitant diseases are treated to reduce blood pressure and cardiovascular risk factors.

3.3 Compound 21

C21 is a first-in-class, low molecular weight, orally available, potent, and selective angiotensin II type 2 receptor agonist (ATRAG) in clinical development for treatment of rare lung diseases, including idiopathic pulmonary fibrosis (IPF).

[figure not shown]
C21 has been granted orphan drug designation in IPF by the European Medicines Agency (EMA) and the United States Food and Drug Administration (FDA).

3.3.1 Non-clinical Data

Vicore Pharma AB Version: 2.0 Trial ID: VP-C21-013 Date: 03-MAR-2023

3.3.2 Clinical Experience

Clinical Trial Protocol

Vicore Pharma AB Version: 2.0
Trial ID: VP-C21-013 Date: 03-MAR-2023

3.4 Rationale for Trial

[figure not shown]
C21 is a first-in-class, low molecular weight, orally available, potent, and selective angiotensin II type 2 receptor agonist (ATRAG) in clinical development for treatment of rare lung diseases, including IPF.

The renin angiotensin system (RAS) is intimately involved in cardiovascular disease where stimulation of the angiotensin II type 1 (AT1) receptor leads to increased blood pressure and, consequently, increased risk of cardiovascular events. The angiotensin II type 2 (AT2) receptor

Clinical Trial Protocol

Vicore Pharma AB Version: 2.0 Trial ID: VP-C21-013 Date: 03-MAR-2023

has an opposite effect and in animal studies it has been shown that stimulation protects against cardiovascular risk in various diabetes models (Steckelings et al., 2022). Endogenous AT2R activation is critically involved in the control of vascular tone by evoking vasodilation in response to flow (shear stress) that in turn opposes active myogenic tone. This flow-mediated increase in vessel diameter, mediated by endothelial-derived NO, is best described for AT2R in the mesenteric circulation (Matrougui et al., 1999).

3.5 Rationale for Trial Design

This is a randomised, double-blind, placebo-controlled, 2-way cross-over trial to evaluate the effect of C21 on endothelial dysfunction and safety in subjects with T2DM.

A cross-over design is applied to control for inter-individual variability.

Randomisation is applied to minimise bias in the assignment of subjects. Double-blinded treatment is applied to reduce potential bias during data collection and evaluation of endpoints.

The timing of the IMP administration in relation to the EndoPAT assessment is based on the pharmacokinetic properties of C21.

Overall, the trial will provide important data to support the design of further clinical trials.

3.6 Rationale for Dose and Dosing Regimen

[figure not shown]
A single dose of 200 mg C21 is selected to achieve a sufficient coverage of the AT2 receptor

3.7 Risk-Benefit Assessment

The subjects participating in this trial will have no medical benefit from participation and their safety and wellbeing are of outmost importance.

Vicore Pharma AB Version: 2.0
Trial ID: VP-C21-013 Date: 03-MAR-2023

Aside from the risks related to C21, as detailed above, there may also be risks related to trial-specific procedures such as the EndoPAT assessment. EndoPAT is a non-invasive method to assess endothelial dysfunction. During the assessment, a blood-pressure cuff is used to achieve and maintain arterial occlusion for 5 minutes. Inflating the cuff might cause some stress and discomfort to the patient, however, the risk associated with its use is considered low and ethically justifiable. Other trial-specific evaluations and sampling procedures, such as blood-pressure measurements using a blood pressure cuff and blood sampling, may cause transient discomfort but the risk is deemed to be low and ethically justifiable. Overall, the combined

Vicore Pharma AB
Trial ID: VP-C21-013
Version: 2.0
Date: 03-MAR-2023

Vicore Pharma AB
Version: 2.0
Trial ID: VP-C21-013
Date: 03-MAR-2023

4 OBJECTIVES AND ENDPOINTS

Primary objective	Endpoints	Assessments	Analysis
To evaluate the pharmacodynamic effect of a single oral dose of 200 mg C21 versus placebo on endothelial dysfunction in subjects with T2DM	RHI score as measured by EndoPAT.	EndoPAT assessment (Section 8.2.1).	Section 13.5
Secondary objectives	Endpoints	Assessments	Analysis
To evaluate the safety of a			
	AI score as measured by EndoPAT.	EndoPAT assessment (Section 8.2.1).	Section 13.5

Clinical Trial Protocol

Vicore Pharma AB Version: 2.0 Trial ID: VP-C21-013 Date: 03-MAR-2023

5 TRIAL POPULATION

Prospective approval of deviations from the eligibility criteria, also known as protocol waivers or exemptions, is not permitted.

5.1 Recruitment

Subjects will be recruited from the trial site's trial database.

5.2 Screening and Enrolment Log

Investigators must keep a record of all screened subjects even if they were not subsequently included in the trial. This information is necessary to verify that subjects were selected without bias.

A screening number will be allocated to each subject in connection to the informed consent process at the screening visit (Visit 1). The screening number will allow identification of subjects irrespective of their possible eligibility for the trial.

Screen failures are defined as subjects who consent to participate in the clinical trial but do not fulfil all eligibility criteria and are not subsequently included in the trial. A minimal set of screen failure information is required to ensure transparent reporting of screen failure subjects. Minimal information includes documentation of signed and dated informed consent form (ICF) and reason(s) for screening failure.

Subjects who do not meet the criteria for participation in this trial may not be rescreened.

5.3 Inclusion Criteria

For inclusion in the trial, subjects must fulfil the following criteria:

- Written informed consent, consistent with ICH-GCP R2 and local laws, obtained before the initiation of any trial-related procedure.
- 2) Male or female patient aged \geq 40 years at the time of the screening visit (Visit 1).
- 3) Documented diagnosed with T2DM prior to the screening visit (Visit 1).
- 4) An RHI score ≤2 as assessed by EndoPAT at the time of the screening visit (Visit 1).
- 5) Contraceptive use by men and women of childbearing potential which is highly effective and consistent with local regulations regarding the methods of contraception for those participating in clinical trials.

5.4 Exclusion Criteria

Subjects must not enter the trial if any of the following exclusion criteria are fulfilled:

Concurrent serious medical condition which in the opinion of the investigator constitutes a
risk or a contraindication for the participation in the trial or that could interfere with the trial
objectives, conduct or evaluation.

Vicore Pharma ABVersion: 2.0Trial ID: VP-C21-013Date: 03-MAR-2023

- 2) Known, active hepatitis B, C, or human immunodeficiency virus (HIV) infection (*i.e.*, HIV with a CD4 count <500 cells/mm³).
- 3) Impaired hepatic function or clinically significant liver disease, which in the investigator's opinion makes the subject inappropriate for this trial.
- 4) Severe renal impairment (*i.e.*, estimated glomerular filtration rate (eGFR) ≤30 mL/min/1.73 m²).
- 5) Prolonged QTcF (QT interval with Fridericia's correction) (>450 ms), atrial fibrillation, clinically significant arrhythmia or other clinically significant abnormality in the resting ECG at screeening (Visit 1), as judged by the investigator.
- 6) Unstable or deteriorating cardiac condition.
- 7) History of severe allergy/hypersensitivity or ongoing allergy/hypersensitivity, as judged by the investigator, or history of hypersensitivity to drugs with a similar chemical structure or class to any of the IMPs.
- 8) Pregnant or breast-feeding female subjects.
- 9) Malignancy within the past 5 years with the exception of in situ removal of basal cell carcinoma and cervical intraepithelial neoplasia grade I.
- 10) Planned major surgery within the duration of the trial.
- 11) Treatment with the medications listed below within 14 days prior to screening (Visit 1) or anticipated need for such medication during the participation in this trial:
 - Insulin.
 - Glucagon-like peptide-1 (GLP-1) agonists.
 - Strong Cytochrome P450 (CYP) 3A4 inducers (e.g., rifampicin, phenytoin, carbamazepine and St. John's Wort).
 - Strong CYP 3A4 inhibitors (*e.g.*, clarithromycin, ketoconazole, nefazodone, itraconazole, ritonavir).
 - Warfarin, digoxin and other medication where the dose needs to be individually titrated.
 - Narrow therapeutic index drugs that are substrates of CYP1A2, CYP2C8, CYP2C9, CYP2C19, CYP3A4, or OATP1B1.
- 12) Current or previous participation in any other clinical trial where the subject has received a dose of IMP within 1 month or 5 half-lives of the IMP, whichever is longest, prior to screening.
- 13) Abnormal laboratory value at screening indicating a potential risk for the subject if enrolled in the trial as evaluated by the investigator.

5.5 Restrictions During the Trial

Subjects must be willing to comply with the restrictions as outlined in Sections 5.5.1 and 5.5.2.

Clinical Trial Protocol

Vicore Pharma AB Version: 2.0 Trial ID: VP-C21-013 Date: 03-MAR-2023

5.5.1 General Restrictions

1. Contraception requirements: Women of child bearing potential (WOCBP) must practice abstinence (if that is their preferred lifestyle) from Visit 1 to Visit 4, or must agree to use a highly effective method of contraception with a failure rate of <1% to prevent pregnancy (combined [oestrogen and progestogen containing] hormonal contraception associated with inhibition of ovulation [oral, intravaginal, transdermal], progestogen-only hormonal contraception associated with inhibition of ovulation [oral, injectable, implantable], intrauterine device [IUD] or intrauterine hormone-releasing system [IUS]) from at least 4 weeks prior to the first IMP administration until 4 weeks after last IMP administration. Their male partner must agree to use a condom during the same time frame, unless he has had a demonstrated successful vasectomy more than 6 months ago.

Males should use condom and their female partner of child-bearing potential must use a contraceptive method with a failure rate of <1% to prevent pregnancy (see above) and drug exposure of a partner and refrain from donating sperm from the date of dosing until 3 months after the last IMP administration.

- 2. Meals and dietary restrictions: Subjects must fast for at least 3 hours prior to admission to the trial site for Visits 2 and 3, and until end of the EndoPAT assessment. Water is allowed *ad libitum*, except for 1 hour before and 1 hour after IMP administration.
- 3. Alcohol: Consumption of alcohol is not allowed from 12 hours prior to admission to the trial site for Visits 2 and 3, and during these visits.
- 4. Coffee, tea, and other caffeine-containing beverages: No coffee, tea or other caffeine-containing beverages are allowed from 2 hours prior to admission to the trial site for Visits 2 and 3, and until end of the EndoPAT assessment.
- 5. Taurine-containing beverages: Beverages containing taurine, *e.g.*, energy drinks such as Red Bull and Monster Energy, are not allowed from 2 hours prior to admission to the trial site for Visits 2 and 3, and until the end of the EndoPAT assessment.
- 6. Nicotine: Smoking or the use of nicotine-containing products, including non-tobacco oral nicotine products, is not allowed from 3 hours prior to admission to the trial site for Visits 2 and 3, and until end of the EndoPAT assessment.
- 7. Grapefruit and grapefruit-containing products: The consumption of grapefruit and/or grapefruit-containing products such as jams, jellies, preserves, and fruit juices is not allowed from 12 hours prior to until 12 hours after IMP administration at Visits 2 and 3.
- 8. Exercise: Subjects must refrain from strenuous exercise, defined as greater than 70% of the maximal pulse rate for 1 hour or more, for at least 12 hours prior to admission to the trial site for Visits 2 and 3, and until end of the EndoPAT assessments.
- 9. Blood donation: Subjects must not donate blood or plasma from the screening visit until 3 months after the final medical examination at the end-of-trial visit.
- 10. Participation in other clinical trials: Subjects are not allowed to participate in any other interventional clinical trial from the screening visit until the end-of-trial visit.

Clinical Trial Protocol

Vicore Pharma AB Version: 2.0 Trial ID: VP-C21-013 Date: 03-MAR-2023

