8.3 Safety Assessments

8.3.1 Adverse Events

Adverse events (AEs) will be reported from signing of informed consent until end-of-trial participation (Visit 4).

At Visits 2 and 3, the subjects will be asked about AEs at admission to the trial site and just before discharge.

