9.2 Other Reportable Information

Certain information although not consistent with an SAE must be recorded, reported, and followed up in the same way as an SAE. This includes:

Vicore Pharma AB Version: 2.0 Trial ID: VP-C21-013 Date: 03-MAR-2023

- Any pregnancy that occurs during trial participation must be reported and administration of IMP must be terminated immediately. A pregnancy must be reported immediately to sponsor or designee. The pregnancy must be followed up to determine outcome including premature termination and status of mother and infant. The outcome must be reported even if there are no abnormal findings. Pregnancy complications and elective terminations for medical reasons must be reported as AEs or SAEs, as applicable. Spontaneous abortion must be reported as an SAE. In addition, the investigator must attempt to collect pregnancy information on any female partners of male trial participants who become pregnant while the male participant is enrolled in the trial. Pregnancy information must be reported to sponsor as described above.
- Lactation exposure to and IMP with or without an AE.
- Overdose of an IMP with or without an AE.
- Inadvertent or accidental exposure to an IMP with or without an AE.

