9.4 Recording of Adverse Events

All events meeting the definition of an AE must be reported in the period from the subject has signed the informed consent form until the end-of-trial participation (Visit 4).

At each visit the subject will be asked about AEs in an objective manner, e.g.: "Have you experienced any problems since the last visit?". They will also be asked if they have been hospitalized, had any accidents, usen any new medications, or changed concomitant medication regiments (both prescription and over the counter medication).

Only medically qualified personnel are allowed to assess AEs.

AEs must be reported on the AE page of the eCRF. The diagnosis should be recorded, if available. If no diagnosis is available each sign and symptom should be recorded as individual AEs.

Information to be collected includes type of event, time of onset, investigator's assessment of severity and relationship to trial treatment, time of resolution of the event, seriousness, as well as any required treatment or evaluations, and outcome. The AEs resulting from concurrent illnesses, reactions to concurrent illnesses, reactions to concurrent medications, or progression of disease states must also be reported. For follow-up of AEs please refer to Section 9.6.

The Medical Dictionary for Regulatory Activities (MedDRA) will be used to code all AEs.

Any medical condition that is present at the time that the subject is screened for the trial and which does not deteriorate should not be reported as an AE. However, if the condition deteriorates/ worsens at any time during the subject's participation in the trial, it should be recorded as an AE.

Vicore Pharma AB Version: 2.0 Trial ID: VP-C21-013 Date: 03-MAR-2023

Abnormal laboratory values shall be recorded as AEs if assessed as clinically significant by the investigator. In that case, the severity will be assessed as per above. Laboratory abnormalities that are associated with an already reported medical condition will not be reported as separate AEs but will be used for the assessment of the associated medical condition (e.g., increased neutrophil count in case of a reported infection or increased glucose in a patient with diabetes).

Changes in the severity of an AE should be recorded to allow an assessment of the duration of the event at each level of intensity to be performed. An AE characterized as intermittent requires documentation of the onset and duration of each episode.

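### The abstinence duty and, on the natural reading, pregnancy reporting stop at Visit 4, before the protocol's post-dose precaution periods of 4 weeks (women) and 3 months (men) are over

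*Combined protocol and SAP*

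**What the plan says.** Section 5.5.1 gives women of childbearing potential two options in one sentence, each with its own end date. A woman who chooses abstinence "must practice abstinence (if that is their preferred lifestyle) from Visit 1 to Visit 4". A woman who uses contraception must do so "until 4 weeks after last IMP administration". Men are to use condoms, have a partner of childbearing potential use effective contraception, and "refrain from donating sperm from the date of dosing until 3 months after the last IMP administration".

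Section 9.2 sets the reporting duty: "Any pregnancy that occurs during trial participation must be reported". For partners of male subjects, the investigator must try to collect information on those "who become pregnant while the male participant is enrolled in the trial". For a reportable pregnancy the section adds: "The pregnancy must be followed up to determine outcome including premature termination and status of mother and infant".

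Section 9.2 does not say when participation or enrolment ends. Section 8.3.1 says that adverse events "will be reported from signing of informed consent until end-of-trial participation (Visit 4"), and section 9.4 sets the same window, from when the subject has "signed the informed consent form until the end-of-trial participation (Visit 4"). Section 6.1 places Visit 4 at 5 to 14 days after Visit 3, or after early withdrawal. It gives each subject's time in the trial as 9 to 47 days, including screening.

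**The concern.** A post-dose precaution period is the sponsor's own statement of how long conception should be avoided after dosing. Two end dates fall short of it.

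First, two women given the same doses have different end dates according to how they avoid pregnancy, and the visible text gives no reason.

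Second, the duty to report a pregnancy appears to end while precautions still apply. A pregnancy conceived after Visit 4, but inside the precaution period, would then need neither reporting nor follow-up to outcome. That includes a spontaneous abortion, which section 9.2 otherwise makes reportable as a serious adverse event.

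What is at stake is completeness of safety information, not the efficacy comparison.

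**Working it through.** The plan states no figure for this gap, so there is none to reproduce. The check compares time windows.

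**Inputs**
- Last dose for a completer: Visit 3 (Table 1).
- Visit 2 to Visit 3: 3 to 14 days (section 6.1).
- Visit 4: 5 to 14 days after Visit 3, or after early withdrawal (section 6.1).
- Women's contraception limit: 4 weeks = 28 days after the last dose (section 5.5.1).
- Men's limit: 3 months after the last dose (section 5.5.1), taken as 90 days.

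**Formula:** gap = end of precaution period − day of Visit 4, both counted from the same dose.

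| Case | Visit 4, days after the dose | Women's gap (days) | Men's gap (days) |
|---|---|---|---|
| Completers, from last dose (the rule as written) | 5 to 14 | 28−14 = 14 to 28−5 = 23 | 90−14 = 76 to 90−5 = 85 |
| Withdrawn after Visit 2, from the only dose | 0+5 = 5 to 14+14 = 28 | 28−28 = 0 to 28−5 = 23 | 90−28 = 62 to 90−5 = 85 |
| C21-first completers, from the C21 dose | 3+5 = 8 to 14+14 = 28 | 28−28 = 0 to 28−8 = 20 | 90−28 = 62 to 90−8 = 82 |

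The second row assumes withdrawal 0 to 14 days after the dose, with the Visit 4 window running from withdrawal. The third row is a sensitivity check, because the protocol counts from the last dose of either product. If 3 months is taken as 89 to 92 days, the completers' figure for men becomes 89−14 = 75 to 92−5 = 87.

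**Does enrolment reach the end of the precaution period?** Section 6.1 allows at most 47 days per subject including screening (the visit windows themselves add to 21+14+14 = 49). Either figure is below 90, so 3 months after the last dose cannot lie within enrolment. For women, the link from section 9.2 to Visit 4 rests on sections 8.3.1 and 9.4.

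**Does other text close the gap?**
- Inclusion criterion 5 requires contraception but gives no end date.
- Table 1 schedules no contact or pregnancy test after Visit 4.
- Section 9.6 continues follow-up after the trial only for ongoing serious events and for severe non-serious events considered related.
- The follow-up to outcome in section 9.2 applies to a pregnancy that is already reportable. One that occurs before Visit 4 and is found later is therefore covered; one conceived after Visit 4 is not.

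**The case against.** The strongest reply is that the reporting cut-off is inferred. Section 9.2 exempts nothing and does not name Visit 4; sections 8.3.1 and 9.4 concern adverse events. That stands as a caveat. Even so, both duties in section 9.2 are tied to participation or enrolment, and the stated trial duration rules out any reading that reaches 3 months.

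Other points limit the weight:

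- **Abstinence.** It is allowed only for women whose usual way of life it is, and such subjects may number zero. This part is a missing obligation, not shown exposure.
- **The men's 3 months.** The end date follows directly on the sperm-donation clause. Reading it as also covering condoms and partner contraception is reasonable, since the sentence gives no other end date, but it is a reading. The women's gap does not depend on it.
- **Accidental exposure.** Section 9.2 also makes accidental exposure to the product reportable, with no time limit, and a partner's exposure might be reported that way. It does not create a duty to report a pregnancy.
- **Residual risk.** Women of childbearing potential are tested at every visit, so what remains is conception at least 5 days after the last dose. Each subject gets one C21 dose, and the sponsor accepts a washout as short as 3 days. The basis for the 4-week and 3-month periods is not visible in this copy, so their necessity cannot be tested.
- **Rescheduling.** Section 5.5.2 lets a visit be moved once, by less than 10 days. If that can push Visit 3 past day 14, Visit 4 could fall up to almost 14+10+14 = 38 days after the first dose. The 62-day minimum in the second and third rows would then drop to just over 90−38 = 52 days. The completers' figures from the last dose do not change.
- **Unseen forms.** The consent form and the serious adverse event form were not available and may carry post-trial instructions.

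**Conclusion.** The concern holds and is minor. The different end dates for abstinence and contraception are plain on the text. The reporting gap follows if participation and enrolment end at Visit 4, which is the natural reading.

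The women's shortfall is certain for completers counted from the last dose, but can shrink to nothing after early withdrawal or when counted from C21. The men's gap stays large in every case examined, provided the 3-month clause covers all the male precautions.

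No harm is shown. With 10 to 14 subjects aged 40 or over, few women of childbearing potential are likely, and the RHI comparison is untouched. The point matters because the rules, followed exactly, drop safety information within the sponsor's own precaution period.

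**What to change.** In section 5.5.1, extend abstinence to 4 weeks after the last dose, the same end date as for contraception users. In section 9.2, require reporting of pregnancies occurring up to 4 weeks after the last dose in female subjects and up to 3 months after it in partners of male subjects, and have subjects told to notify the site.

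The cost is protocol wording, consent wording if the form does not already cover it, and reliance on self-report after Visit 4. No visits are added. The protocol already places a duty on subjects after Visit 4: the blood-donation restriction in section 5.5.1 lasts 3 months beyond the end-of-trial examination. The different start dates for abstinence and contraception are a separate matter and need no change for this point.
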